### 13.2. Assessing Adverse Events

In conjunction with the medical monitor, the Investigator will evaluate adverse events to ensure the events are categorized correctly. Elements of categorization will include:

- Seriousness/Classifications (see definition in Section 13.1)
- Causality or Relatedness – i.e. the relationship between the Test article, study treatment or study procedures and the adverse event (not related; unlikely related; possibly related; related - see definition in Section 13.2.1)
- Adverse Event Severity – Adverse event severity is used to assess the degree of intensity of the adverse event (mild; moderate; severe for all events - see definition in Section 13.2.2).

[REDACTED] (5)

- Outcome – Not Recovered or Not Resolved; Recovering or Resolving; Recovered or Resolved with Sequelae; Recovered or Resolved; Death Related to Adverse Event; Unknown
- Actions Taken – None; temporarily discontinued; permanently discontinued; other action taken

### 13.2.1 Causality Assessment

**Causality Assessment** – A determination of the relationship between an adverse event and the Test article, study treatment, or study procedure. The Test article, study treatment or study procedure relationship for each adverse event shall be determined by the Investigator using these explanations:

- Not Related- An adverse event that is not related to the use of the test article, study treatment or study procedures.
- Unlikely Related – An adverse event for which an alternative explanation is more likely, e.g. concomitant treatment, concomitant disease(s), or the relationship of time suggests that a causal relationship is unlikely.
- Possibly Related – An adverse event that might be due to the use of the test article, or to the study treatment or study procedures. An alternative explanation, e.g. concomitant treatment, concomitant disease(s), is inconclusive. The relationship in time is reasonable. Therefore, the causal relationship cannot be excluded.
- Related – An adverse event that is listed as a possible adverse effect (device) or adverse reaction (drug) and cannot be reasonably explained by an alternative explanation, e.g. concomitant treatment of concomitant disease(s). The relationship in time is very suggestive, e.g. it is confirmed by de-challenge and re-challenge.

### 13.2.2 Severity Assessment

**Severity Assessment** – A qualitative assessment of the degree of intensity of an adverse event as determined by the Investigator or reported to him/her by the subject. The assessment of severity is made irrespective of Test article, study treatment or study procedure relationship or seriousness of the event and should be evaluated according to the following scale:

- Mild – Event is noticeable to the subject, but is easily tolerated and does not interfere with the subject's daily activities
- Moderate – Event is bothersome, possible requiring additional therapy, and may interfere with the subject's daily activities
- Severe – Event is intolerable, necessitates additional therapy or alteration of therapy and interferes with the subject's daily activities

### 13.3. Documentation and Follow-Up of Adverse Events

The recording and documenting of adverse events (ocular and non-ocular) begins when the subjects are exposed to the Test article, study treatment or study procedure. Adverse events

reported before the use of Test article, start of study treatment, or study procedures will be recorded as medical history. However, if the condition deteriorates at any time during the study it will be recorded and reported as an AE. Untoward medical events reported after the subject's exit from the study will be recorded as adverse events at the discretion of the Investigator.

Upon finding an adverse event, the Principal Investigator will document the condition in the subject record and in the eCRFs. He/she will complete the Adverse Event /eCRF.

Complete descriptions of all adverse events must be available in the subject record. All Adverse Events including local and systemic reactions not meeting the criteria for "serious adverse events" shall be captured on the appropriate case report form or electronic data system. All adverse events occurring while the subject is enrolled in the study must be documented appropriately regardless of relationship.

It is the Investigator's responsibility to maintain documentation of each reported adverse event. All adverse events will be followed in accordance with applicable licensing requirements. Such documentation will include the following:

- Adverse event (diagnosis not symptom)
- Drawings or photographs (where appropriate) that detail the finding (e.g., size, location, and depth, etc.)
- Date the clinical site was notified
- Date and time of onset
- Date and time of resolution
- Adverse event classification, severity, and relationship to Test articles, as applicable
- Treatment regimen instituted, including concomitant medications prescribed, in accordance with applicable licensing requirements
- Any referral to another health care provider if needed
- Outcome, ocular damage (if any)
- Likely etiology
- Best corrected visual acuity at the discovery of the event and upon conclusion of the event

In addition, if an infiltrate(s) is present, he/she will complete the Corneal Infiltrate Assessment /eCRF. Where necessary, a culture of the corneal lesion will be collected to determine if the infection is microbial in nature. If cultures are collected, the date of culture collection and laboratory utilized will be recorded.

Changes in the severity of an AE shall be documented to allow an assessment of the duration of the event at each level of intensity to be performed. Adverse events characterized as

[REDACTED] (5)

intermittent require documentation of the onset and duration of each episode. Changes in the assessment of relationship to the Test Article shall also be clearly documented.

Subjects who present with an adverse event shall be followed by the Investigator, within licensure, until all signs and symptoms have returned to pre-treatment status, stabilized, or been satisfactorily resolved. If further treatment beyond licensure is required, the patient will be referred to the appropriate health care provider. The Investigator will use his/her clinical judgment as to whether or not a subject reporting with an adverse event will continue in the study. If a subject is discontinued from the study, it will be the responsibility of the Investigator to record the reason for discontinuation. The Investigator will also document the adverse event appropriately and complete the Adverse Event /eCRF. Any subjects with ongoing adverse events related to the Test article, study treatment or study procedures, as of the final study visit date should be followed to resolution of the adverse event or until referral to an appropriate health care provider, as recommended by the Investigator.

#### **13.4. Reporting Adverse Events**

The Investigator will notify the Sponsor of an adverse event by e-mail, facsimile, or telephone as soon as possible and no later than 24 hours from discovery for any serious /significant adverse events, and 2 days from discovery for any non-significant adverse event. In addition, a written report will be submitted by the Principal Investigator to the IEC/IRB according to their requirements (Section 13.4.2). The report will comment whether or not the adverse event was considered to be related to the Test article, study treatment or study procedures.

##### **13.4.1 Reporting Adverse Events to Sponsor**

###### **Serious/Significant Adverse Events**

The Investigator will inform the sponsor of all serious/significant adverse events occurring during the study period as soon as possible by e-mail, fax, or telephone, but no later than 24 hours following discovery of the event. The Investigator is obligated to pursue and obtain information requested by the Sponsor in addition to that information reported on the eCRF. All subjects experiencing a serious/significant adverse event must be followed up and all outcomes must be reported.

When medically necessary, the Investigator may break the randomization code to determine the identity of the treatment that the subject received. The Sponsor and study monitor should be notified prior to unmasking the Test articles.

In the event of a serious/significant adverse event, the Investigator must:

- Notify the Sponsor immediately

[REDACTED] (5)

- Obtain and maintain in the subject's records all pertinent medical information and medical judgment for colleagues who assisted in the treatment and follow-up of the subject
- Provide the Sponsor with a complete case history which includes a statement as to whether the event was or was not related to the use of the Test article
- Notify the IEC/IRB as required by the IEC/IRB reporting procedure according to national regulations

### **Unanticipated (Serious) Adverse Device Effect (UADE)**

In the event of an Unanticipated (Serious) Adverse Device Effect (UADE), the Investigator will submit a report of the UADE to the Sponsor and IEC/IRB as soon as possible, but no later than 24 hours after the Investigator first learns of the effect. This report is in addition to the immediate notification mentioned above.

The Sponsor must conduct an evaluation of the UADE and must report the results of the evaluation to FDA, the IEC/IRB and participating Investigators within 10 working days after the Sponsor first receives notification of the effect.

### **Non-Serious Adverse Events**

All non-serious adverse events, including non-serious adverse device effects, will be reported to the sponsor by the Investigator no later than 2 days from discovery.

#### **13.4.2 Reporting Adverse Events to the Responsible IEC/IRB and Health Authorities**

Adverse events that meet the IEC/IRB requirements for reporting must be reported within the IEC/IRB's written guidelines. Each clinical site will refer to and follow any guidelines set forth by their Approving IEC/IRB. Each clinical site will refer to and follow any guidelines set forth by their local governing Health Authorities.

The Sponsor will report applicable Adverse Events to the local health authorities according the written guidelines, including reporting timelines.

#### **13.5. Event of Special Interest**

None

#### **13.6. Reporting of Pregnancy**

Subjects reporting pregnancy (by self-report) during the course of the study will be discontinued after the event is recorded as an Adverse Event. Once discontinued, pregnant participants and their fetuses will not be monitored for study related purposes. At the Investigator's discretion, the study participant may be followed by the Investigator through delivery. However, this data will not be collected as part of the clinical study database. Pregnant participants are not discontinued from contact lens or solution related studies for

safety concerns, but due to general concerns relating to pregnancy and contact lens use. Specifically, pregnant women are discontinued due to fluctuations in refractive error and/or visual acuity that occur secondary to systemic hormonal changes, and not due to unforeseen health risks to the mother or fetus.

## 14. STATISTICAL METHODS

### 14.1. General Considerations

All data summaries and statistical analyses will be performed using the SAS software Version 9.4 (SAS Institute, Cary, NC). Throughout the analysis of data, the results for each subject/eye will be used when available for summarization and statistical analysis. Unscheduled visits will be summarized separately and will be excluded from the statistical analysis.

Summary tables (Descriptive statistics and/or frequency tables) will be provided for all baseline variables, efficacy variables and safety variables as appropriate. Continuous variables will be summarized with descriptive statistics (n, mean, standard deviation (SD), median, minimum and maximum). Frequency count and percentage of subjects or eyes within each category will be provided for categorical data.

Summaries will be presented by study lens type and will be performed separately by completion status. All analyses will be conducted on per-protocol population (see section 14.3).

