#### **Other Observation(s)**

### **2.3. Hypotheses**

#### **Primary Hypotheses**

The maximum number of modification required by the ECP to optimize vision will not exceed one modification in more than 50% of the subjects.

Secondary Hypotheses  
Not Applicable

Other Hypotheses  
Not Applicable

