1.13	Add Refinement	Place the BCC result in the trial frame and refine the near prescription with trial lenses (or flippers) under binocular conditions.	
1.14	Near Visual Acuity	Using the ETDRS 2000 Series Chart 1 or 2 near card placed at 40 cm. Record the near visual acuity OD, OS and OU at 40 cm.	
1.15	Biomicroscopy	
FDA Slit Lamp Classification Scale will be used to grade the findings and determine eligibility.
 
For the conjunctival redness [REDACTED] 0.5 unit increments will be used in the grading. Corneal Staining Assessment [REDACTED] will be graded in 1.0 increments.
 
If any of these slit lamp findings are Grade 3 or higher, the subject will be discontinued. If discontinued a final examination must be completed.
 
If the clearance of the fluorescein needs to be expedited, preservative-free rewetting drops or saline may be instilled.
	
1.16	Eligibility after Baseline	All responses to Inclusion Criteria questions must be answered "yes" and all responses to Exclusion Criteria questions must be answered "no" for the subject to be considered eligible.	

Visit 1: Treatment 1 Lens Fitting			
Step	Procedure	Details	
1.17	ECP Global ID	ADD the ECP's global ID.	
1.18	ECP Lens Selection	The ECP will be provided with the fitting guide and determine the initial study lens selection. The study staff will select the lens pair and power for each eye. Record the test	Appendix F/G Fitting Guides

		lens parameters (power and lot number).	
1.19	Lens insertion	
Subjects will insert the lenses themselves. If the lens is uncomfortable, inspect for damage and remove, reinsert or replace as necessary. Damaged lenses will be stored in labeled vial with sterile saline, and clearly differentiated from the other worn lenses that will be shipped back to the Sponsor. Complete the Quality Product Complaint form.
	
1.20	Toric Fit Evaluation (if applicable)	
The principal or Co-Investigator will evaluate the toric fit and record:
 
 
• The rotational position to the nearest degree
 
• Lens stability with blink
 
• Lens stability with eye versions
 
• Toric fit acceptable or unacceptable
 
 
Toric lens fit will be unacceptable if lenses rotated more than 40 degrees, or lens stability is worse than 5 degrees movement with blink. If toric fit is unacceptable, remove the lenses, perform biomicroscopy and proceed to final evaluation.
	

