1.21	Lens Fit Assessment	
The principal or Co-Investigator will evaluate the general lens fit. Lens fit will be assessed in primary gaze, upgaze & Josephson push up test.
 
An unacceptable lens fit will be any one or more of the following:
 
 
• presence of limbal exposure (appearance of clear cornea) in any gaze
 
• presence of edge lift
 
• Presence of unacceptable movement (excessive or insufficient) in all three movement categories (primary gaze, upgaze, and push-up).
 
 
If either lens is deemed unacceptable, the subject will be discontinued from the study. Perform a slit-lamp evaluation and complete the Final Evaluation
	

████████ (5)

1.22	Lens Settling	Allow the study lenses to continue to settle for a minimum of 15 minutes from the time of lens insertion	
1.23	ECP Fitting with Fit Guide	The ECP will be provided the fitting guides and assess the vision provided by the lenses and will determine if a lens change is needed. The fitting activities of the ECP will be videotaped. During the fitting of the lenses the ECP may use the slit lamp to evaluate the fit of the lens. .	Appendix F/G Fitting Guides
1.24	Modifications (if necessary)	If the ECP determines a change in lenses is required they will be allowed two Modifications. If modification is needed complete steps 1.18 to 1.19 for each lens change.	Appendix F/G Fitting Guides
1.25	Post-Fit Questionnaire	The subject will evaluate the vision characteristics, comfort characteristics, handling characteristics, and visual symptoms of the study lenses using the PRO questionnaire. Subjects will also be shown a product concept of the lens they have just worn and their feedback regarding the concept will be collected.	Appendix A and H
1.26	Exit Biomicroscopy	The Principal Investigator or Co-Investigator will perform biomicroscopy OD and OS. Slit Lamp Classification Scales will be used to grade the findings. For the conjunctival redness [REDACTED] 0.5 unit increments will be used in the grading. Corneal Staining Assessment [REDACTED] will be graded in 1.0 increments.	[REDACTED]
1.27	ECP Interview	The ECP will be interviewed regarding their experience fitting the subject using the Fit Guide.	Appendix I

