### **8.2. Withdrawal/Discontinuation from the Study**

A subject will be withdrawn from the study for any of the following reasons:

- Subject death during the study period
- Subject withdrawal of consent
- Subject not compliant to protocol
- Subject lost to follow-up
- Subject no longer meets eligibility criteria (e.g. the subject becomes pregnant)
- Subject develops significant or serious adverse events causing discontinuation of study lens wear
- Subjects who have experienced a Corneal infiltrative Event (CIE)
- Investigator's clinical judgment regarding the subject safety reasons (that it is in the best interest of the subject to stop treatment)
- Subject not compliant with study lens wear schedule
- Subject not successfully dispensed due to lack of efficacy and safety including poor vision, poor comfort or unacceptable fit

For discontinued subjects, the Investigator will:

- Complete the current visit (scheduled or unscheduled)
- Complete the Final Evaluation, indicating the reason that the subject was discontinued from the study
- Record the spherocylindrical refraction with best corrected distance visual acuity
- Collect used Test article(s) (worn or brought to the visit) from the subject and discard them, unless otherwise stated in Section 7.2
- Collect all unused Test article(s) from the subject

An additional subject may be enrolled if a subject discontinues from the study prematurely.

In cases where a subject is lost to follow-up, every possible effort must be made to contact the subject and determine the reason for discontinuation/withdrawal. The measures taken to follow up must be documented including two written attempts and a certified letter (or equivalent) as the final attempt.

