**Per-Protocol Population:**

All subjects who have successfully completed all visits and did not substantially deviate from the protocol as determined by the trial cohort review committee prior to database hard lock (Per-Protocol Population). Justification of excluding subjects with protocol deviations in the per-protocol population set will be documented in a memo to file.

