#### **14.5. Primary Analysis**

Primary efficacy analysis:

Due to the potential low incidence rates of unacceptable lens fitting, summary statistics will be firstly used to evaluate the percentage of the subjects with at most one optimization per-protocol population.

Due to the potential low incidence rates of unacceptable lens fitting, summary statistics will be firstly used to evaluate the percentage of the subjects with at most one optimization per-protocol population.

If applicable, a generalized linear mixed model with a binary distribution and logit link function will be applied to the number of modifications (1=at most one modification; 0 = more than one modification). Age, gender and subjects' add power will be included in the model as fixed effects when appropriate. ECP and subject will be included as random effect.

The proportion of subjects with at most one optimization will be calculated with 95% confidence interval. If the lower limit of the confidence interval is greater than 50%, the statistical superiority will be concluded.

[REDACTED] (5)

If the incidence rate is too low or there are problems with the convergence of the above model, Agresti methods or Fisher's exact test for binomial proportion will be used to evaluate the confidence intervals of the corresponding endpoints.

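### The primary decision uses per-protocol completers only, and the plan does not say how subjects stopped for unacceptable lens fit after insertion are scored

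*Combined protocol and SAP*

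**What the plan says.** Section 2.3 states the primary hypothesis for the subjects without restriction: "The maximum number of modification required by the ECP to optimize vision will not exceed one modification in more than 50% of the subjects". Section 14.5 codes the outcome as "1=at most one modification; 0 = more than one modification" and concludes superiority if the lower 95% confidence limit for the proportion exceeds 50%.

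The analysis set is named in Section 14.1: "All analyses will be conducted on per-protocol population (see section 14.3". Section 14.3 defines it as "All subjects who have successfully completed all visits and did not substantially deviate from the protocol". Under Section 8.1, a subject withdrawn for a Section 8.2 reason is not a completer, and Section 8.2 lists unacceptable fit among those reasons. It adds: "An additional subject may be enrolled if a subject discontinues from the study prematurely".

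In Section 7.2, lenses are inserted at step 1.19. At step 1.20 the rule is "If toric fit is unacceptable, remove the lenses, perform biomicroscopy and proceed to final evaluation". At step 1.21 it is "If either lens is deemed unacceptable, the subject will be discontinued from the study". The ECP's vision assessment (1.23) and any modification (1.24) come later. A modification repeats only steps 1.18 and 1.19, so a stop at 1.20 or 1.21 always precedes the first modification.

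Section 14.9 leaves missing values unimputed. It adds a multiple-imputation sensitivity analysis only if dropout exceeds 15%.

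**The concern.** The trial makes one inferential decision: whether more than half of the subjects need at most one modification. A subject whose study lens was inserted and then judged not to fit is removed from that decision and may be replaced by someone else. The code in Section 14.5 has no value for this subject. On a literal count there were zero modifications, which is a success. The Synopsis, however, defines the endpoint as modifications needed to optimize the lenses for vision, and that process never began.

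The two readings move the estimate in opposite directions. If these exits are non-successes, dropping them biases the reported proportion upward. If the rule is left open until the data are seen, a few subjects could decide the claim after the fact. Subjects with two modifications are not part of the gap, because the code already scores them 0.

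**Working it through.** **Inputs.** About 32 enrolled and 24 completing (Synopsis, Sections 4.3 and 14.2); the threshold and 95% interval (Section 14.5); the 15% trigger (Section 14.9). The number of fit exits, d, is not given. It is an assumption and is varied below.

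**The plan's own figures.** The Section 14.2 table reproduces with an exact binomial test of 50% at one-sided 5%.
- n = 56, at least 35 successes, true rate 70%: power 0.913.
- n = 35, at least 23, true rate 75%: power 0.924.
- n = 23, at least 16, true rate 80%: power 0.928.

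The table says nothing about fit exits.

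**Lower limits.** With x successes among n, the exact 95% lower limit is the 2.5% quantile of Beta(x, n − x + 1). Agresti-Coull is shown beside it. Section 14.5 names exact and Agresti methods as fallbacks if the mixed model fails, so they only illustrate size here. Exits scored as non-success change x/24 to x/(24 + d).

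| Result | Exits added | Exact | Agresti-Coull |
|---|---|---|---|
| 18/24 | 0 | 53.3% | 54.8% |
| 18/25 | 1 | 50.6% | 52.2% |
| 18/26 | 2 | 48.2% | 49.9% |
| 19/24 | 0 | 57.8% | 59.1% |
| 19/26 | 2 | 52.2% | 53.7% |
| 19/27 | 3 | 49.8% | 51.4% |
| 20/24 | 0 | 62.6% | 63.5% |
| 20/28 | 4 | 51.3% | 52.8% |
| 20/29 | 5 | 49.2% | 50.6% |

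By exact limits, 18/24 is reversed by two exits, 19/24 by three and 20/24 by five. By Agresti-Coull, 18/26 also fails, but 19/27 and 20/29 still pass.

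**Opposite scoring.** 17/24 fails by the exact limit (48.9%). Two exits counted as successes give (17 + 2)/(24 + 2) = 19/26, which passes (52.2%).

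**Chance of a false claim.** Suppose the true success rate among N = 24 + d lens-inserted subjects is 50% and every exit is a non-success. The rate among the 24 completers is then q = 0.5 × (24 + d)/24. The exact rule needs at least 18 of 24. P(X ≥ 18 | 24, q) is 1.1%, 1.9%, 3.0%, 4.7% and 7.1% for d = 0, 1, 2, 3 and 4.

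**Does Section 14.9 close the gap?** If fit exits are the only loss, 2/26 = 7.7% and 3/27 = 11.1% are below 15%, so the sensitivity analysis does not run. If all planned non-completers count as dropouts, (32 − 24)/32 = 25% and it does run. Even then it treats a fit exit as a missing value to be predicted, not as an outcome with a stated score, and it does not enter the decision rule.

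**The case against.** The best defence is that the per-protocol restriction is a legitimate choice of what to estimate. The endpoint concerns modifications to optimize vision. The checks at 1.20 and 1.21 are mechanical and are made by the investigator, before the ECP assesses vision. A subject stopped there never enters the process being measured. This stands, so the documents do not compel scoring these exits as failures. On the other side, the ECP chose the initial lens with the guide at step 1.18, and Section 1 gives success in fitting as part of the study's aim. Non-success is therefore a reasonable reading too, and the plan should say which one applies.

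A reader might infer that the restriction is concealed. It is not: Sections 14.1 and 14.5 both declare it. What is missing is the scoring rule and a matching limit in Section 2.3.

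A reader might also take exclusion at step 1.20 as certain. That step sends the subject to final evaluation without using the word discontinued, and final evaluation is also the ordinary end of this one-visit study. Exclusion there is inferred from the withdrawal reason in Section 8.2, which is itself phrased in terms of dispensing although the study is non-dispensing.

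Section 14.5 refers to "Due to the potential low incidence rates of unacceptable lens fitting", so few exits are expected. Summaries by completion status (14.1) and the reason recorded at step F.2 give some visibility, but neither affects the decision.

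**Conclusion.** The point holds as a gap in specification that can change the conclusion when the result is close to the threshold. With 24 completers and exact limits, two or three fit exits scored as non-success reverse 18/24 or 19/24. Two scored as successes rescue 17/24. Well above the threshold the effect is small: 20/24 survives four exits.

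This rests on an assumed number of exits and on the fallback interval methods rather than the mixed model, and the reversal of 19/24 depends on which fallback is used. The false-claim figures also require every exit to be a non-success. They pass the 2.5% implied by the lower end of a 95% interval at two exits, and the 5% of Section 14.4 only at four.

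Two stronger readings are not supported. The eight planned non-completers cannot be taken to be fit exits, because the plan gives no reasons for them. Nor does the Section 14.2 table need restating: it is a set of what-if sizes by true percentage, and the section says the sample size was not based on a power analysis.

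**What to change.** Before database lock, state in Sections 14.3 and 14.5 how a subject stopped for unacceptable fit after lens insertion is scored, and whether a stop at step 1.20 counts as discontinuation.

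Report, whatever the dropout rate, the proportion and 95% confidence interval among all eligible subjects in whom a study lens was inserted. Keep replaced subjects in the denominator, and score discontinuation for unacceptable fit or vision as non-success. List discontinuations by the reason recorded at step F.2.

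Then choose one of two courses:
- make this the decision analysis, with the per-protocol result as supportive; or
- keep per-protocol as primary, and limit the hypothesis in Section 2.3 and the conclusion to subjects whose lenses fit physically.

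The cost is some wording, one added table and a possibly lower reported rate. The data are already collected, and no study procedure changes.
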